It has been demonstrated that circulating cell-free DNA from blood can be used to detect tumor-specific genomic alterations in the metastatic setting in various tumor types and that current sequencing technologies allow for rapid identification of a large number of genomic alterations from a modest volume of blood²³⁻⁵. In addition to causing less discomfort for the patient, assessing the genomic alterations in blood likely reflects the mutational landscape of metastatic lesions at different sites and may overcome molecular heterogeneity between various tumor sites and regions. Recent data also indicate that liquid biopsy may be useful for monitoring the development of alterations associated with acquired resistance^{26, 27}.

Genomic Health is developing a next generation sequencing LBMP that assesses genomic alterations in plasma including both established alterations where the benefit of treatment with a targeted agent is supported by level I evidence (if present in the tumor). In addition, the LBMP will assess genes that are targets of therapies in late stage clinical trials and genomic alterations that may be relevant for treatment selection but which are supported by only preliminary or preclinical evidence so far.

The reported concordance for assessing genomic alterations in blood versus tumor tissue varies relatively widely due to multiple factors such as methods used, varying tumor burden

CONFIDENTIAL – PROPRIETARY PROPERTY OF GENOMIC HEALTH, INC.

Study Protocol

(with lower sensitivity in patients with lower tumor burden and earlier stages of disease) and coverage of the regions of interest. It is of clinical importance to characterize the performance of the Genomic Health LBMP in the intended use population by assessing the concordance of key actionable genomic alterations detected in plasma with those found in tissue, the current standard of care (biopsy/cytology/excision).

This study focuses on assessing the concordance between LBMP and tissue biopsy in patients with non squamous NSCLC where the clinical utility of a liquid biopsy based mutation assessment is the highest. In NSCLC, many patients are difficult to biopsy and/or have poor quality tumor material and knowing the status of genomic alterations is necessary to select optimal therapy for patients.

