4. STUDY DESIGN

This is a prospective clinical study to characterize the concordance of key clinically relevant genomic alterations in tumor tissue (biopsy/excision/cytology) and liquid biopsy (blood) using the Genomic Health LBMP in patients with stage IV non squamous NSCLC, that are either newly diagnosed with metastatic disease or progressing on therapy (any line). Tissue biopsy and blood collection (liquid biopsy) should be less than eight weeks apart and with no new systemic antitumoral treatment given in the interval between the tissue biopsy and blood collection. Local assessment of tumor tissue samples will be performed at each participating institution as per their clinical standard of care practices and results from the local assessment of genomic alteration status will be used.

Additionally, detection of *EGFR* T790M alterations in plasma samples will be characterized in patients progressing on EGFR targeted therapy (erlotinib, gefinitib, afatinib).

The study will enroll a total of approximately 310 patients (Figure 1):

- approximately 260 patients with plasma and tissue samples will be enrolled. Initially, approximately 200 patients will be enrolled (First Enrollment Phase) regardless of genomic alteration status in tumor tissue. In order to enroll approximately 69 patients with alterations in *EGFR* and 31 patients with alterations in *ALK* this First Enrollment

CONFIDENTIAL – PROPRIETARY PROPERTY OF GENOMIC HEALTH, INC.

Study Protocol

Phase will be followed by enrollment of patients in a with genomic alterations in *EGFR* and *ALK* (Second Enrollment Phase) as described in Table 2. Patients in both enrollment phases may be either newly diagnosed or progressing on therapy.

- approximately 50 patients with plasma samples (concurrent tumor tissue sample not mandatory) who are progressing on EGFR targeted therapy (erlotinib, gefitinib, afatinib) will be enrolled across the enrollment phases. We expect that approximately 25 of these patients will have T790M alteration.

We anticipate that ~20% of samples may be excluded from analysis due to insufficient DNA yield and/or pre-specified QC criteria.

Table 2: Patient enrollment targets for patients with plasma and tissue samples

[figure not shown]
	All patients	Patients with EGFR alterations*	Patients with ALK alterations*	Patients without EGFR or ALK alterations*

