4.1 Required Procedures at Clinical Sites

Participants who are eligible and consent to participate in the study will provide a venous blood sample (2X 10 mL Streck tubes) at a single study related visit. Participants will have no further visits as part of this study. Participants data will be collected at time of progression or at 12 months after blood sample collection, whichever occurs first and in addition, data will be collected to permit outcome analysis of the interim analysis. Participation in the study will not alter clinical care. All other clinical procedures performed and collection of non-study data will be in accordance with each participating institution’s standard of care. Local assessment of tumor tissue samples will be performed at each participating institution as per their clinical standard of care practices and results from the local assessment of genomic alteration status will be used. Each site will need to provide a single H&E slide to Genomic Health for an independent pathology review.

CONFIDENTIAL – PROPRIETARY PROPERTY OF GENOMIC HEALTH, INC.

	<h2>Study Protocol</h2>
---	-------------------------

Table 3. Requirements by patient category to help identify correct patients and required materials at the single required patient visit. Detailed overview in Table 6 (page 39).

Requirements	Patient Category (see Figure 1)		
	A: Newly diagnosed with stage IV disease	A: Patient progressing on treatment (except if progressing on erlotinib, gefitinib, or afatinib)	B: Patient progressing on erlotinib, gefitinib, or afatinib
Biopsy/cytology/excision performed on primary or metastatic lesion	X		
Biopsy/cytology/excision performed on metastatic lesion		X	Only if available
Local pathology report	X	X	X (original diagnosis)
Local mutation report	X	X	X (original diagnosis)
Provide H&E slide from biopsy/cytology/excision to Genomic Health for independent review	X	X	X
Blood sample (2X 10 mL) collected in Streck tubes	X Prior to initiating new systemic anti-tumor treatment AND no more than 8 weeks after tissue biopsy	X Prior to initiating new systemic anti-tumor treatment AND no more than 8 weeks after tissue biopsy	X Prior to initiating new systemic anti-tumor treatment AND no more than 8 weeks after tissue biopsy only in cases where a biopsy was performed

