The detection of *EGFR* T790M alterations in plasma samples will be characterized descriptively in patients progressing on EGFR targeted therapy (erlotinib, gefitinib, afatinib) (study objective 6.2.6).

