8.7 Sample Size

The sample size considerations for this study were based on the probability of observing PPA/NPA estimates in the anticipated range as well as the size of the confidence intervals around these estimates. To account for possible losses (~20%), approximately 260 patients with plasma and tissue samples will be enrolled to obtain approximately 208 patients with evaluable samples for concordance analyses and 50 patients with plasma samples only will be enrolled to obtain 40 evaluable patients to characterize the detection of *EGFR* T790M alterations in plasma. It is expected that the majority of patients with plasma and tissue samples will be newly diagnosed with stage IV non squamous NSCLC since metastatic lesions are not frequently biopsied.

In patients with plasma and tissue samples, two *EGFR* alterations, L858R and exon 19 deletion, are expected to be observed most often: each with ~45% prevalence in patients with *EGFR*-mutant tumors²⁹. The alteration-specific analyses for these alterations are expected to include ~25 evaluable patients each leading to a total of 50 patients with activating *EGFR* alterations. T790M resistance alteration has a low prevalence in untreated NSCLC³⁰ and hence is expected to be observed relatively rarely.

Figure 2 displays the 20th (blue) and the 30th (green) percentiles of the distribution of positive percent agreement as a function of the sample size using a binomial distribution and assuming a true PPA of 80%. Based on these results, a study with 25 patients with a known alteration will have a 70% probability to observe a PPA estimate

CONFIDENTIAL – PROPRIETARY PROPERTY OF GENOMIC HEALTH, INC.

[figure not shown]

Study Protocol

$\geq 75\%$. A study with 50 patients with a known alteration will have an 80% probability to observe a PPA estimate $\geq 75\%$.

Similar calculations for the true PPA of 90% indicate that a study with 25 marker positive patients will have a 75% probability to observe a PPA estimate $\geq 85\%$ (not shown in figure below). A study with 50 patients with a known alteration will have an 85% probability to observe a PPA estimate $\geq 85\%$.

Figure 2. Percentiles of the PPA estimate as a function of sample size assuming true PPA of 80%*

* Moving average smoother was applied to the estimates based on binomial distribution.
Legend: blue line represents 20% percentile and green line – 30% percentile of PPA estimates.

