If a PPA of 80% is observed in 50 patients with a known alteration, the 95% exact Clopper-Pearson confidence interval will have a lower bound of 0.66 (Table 5). Similar logic applies to the NPA estimates. These calculations were obtained using PASS version 13.

CONFIDENTIAL – PROPRIETARY PROPERTY OF GENOMIC HEALTH, INC.

Study Protocol

Table 5. Lower bound of the 95% Clopper-Pearson confidence interval as a function of observed PPA estimate and sample size.

Observed PPA	Number of patients with detected alterations in tissue				
	20	30	40	50	60
0.90	0.68	0.74	0.76	0.78	0.80
0.85	0.62	0.67	0.70	0.72	0.73
0.80	0.56	0.61	0.64	0.66	0.68
0.75	0.51	0.56	0.59	0.61	0.62

In patients with plasma samples only who are progressing on EGFR targeted therapy (erlotinib, gefitinib, afatinib where tissue sample is not mandatory) approximately 50% of patients are expected to have T790M alteration. If the true probability of T790M alteration in this population is 0.50, we will have an 85% chance of detecting these alterations in 40% to 60% of samples from 40 patients progressing on EGFR targeted therapy (erlotinib, gefitinib, afatinib). In analysis with 40 patients, the width of the 95% confidence interval around the proportion of detected T790M alterations will be 0.32 if alterations are detected in 50% of plasma samples.

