
Patient progressing on EGFR targeted therapy (erlotinib, gefitinib, afatinib).
 
Note: Patients changing EGFR therapy due to toxicity or preference without documented disease progression will not be included.
	
 -Tumor tissue sample (at progression) preferable but not mandatory. -Pathology report from metastatic lesion at progression if available and from primary tumor if not available -Mutation report from metastatic lesion at progression if available and from primary tumor if not available -Blood sample in Streck tubes (2X 10 mL) 	
 -Date of progression on first therapy initiated after liquid biopsy, one year after liquid biopsy if still responding, or date of patient death should that occur prior to first progression or 1 year after liquid biopsy. -Clinical and selected treatment data entry in EDC

CONFIDENTIAL – PROPRIETARY PROPERTY OF GENOMIC HEALTH, INC.

Study Protocol

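### As specified for objective 6.2.6, a T790M-negative plasma without tissue at progression cannot be told from a sample with too little tumor DNA, and the 85% in section 8.7 assumes perfect plasma detection

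*Combined protocol and SAP*

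**What the plan says.** **Analysis.** Section 8.4 gives objective 6.2.6 one sentence: EGFR T790M "alterations in plasma samples will be characterized descriptively in patients progressing on EGFR targeted therapy". Section 8.1 leaves further detail to a SAP, which is not in the text supplied.

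**Cohort.** Section 8.7 plans that "50 patients with plasma samples only will be enrolled to obtain 40 evaluable patients". Sections 5.1.3 and 4.1 ask for tissue at progression only where it exists.

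**Planning figures.** Section 8.7 states that "approximately 50% of patients are expected to have T790M alteration" and derives from this an "85% chance of detecting these alterations in 40% to 60% of samples from 40 patients". It gives a 95% interval width of 0.32 if half of the plasmas are positive.

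**Exclusions and assay.** Section 4 anticipates that about "20% of samples may be excluded from analysis due to insufficient DNA yield and/or pre-specified QC criteria". Sections 3 and 8.1 make each result binary. Section 2 acknowledges that plasma performance varies with tumor burden, "with lower sensitivity in patients with lower tumor burden and earlier stages of disease".

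**What is collected.** For category B, Appendix II lists a "Mutation report from metastatic lesion at progression if available and from primary tumor if not available". Table 3 lists the report from original diagnosis. Table 1 shows that the panel reads EGFR SNVs and indels, so the common sensitizing alterations are assayed alongside T790M.

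**The concern.** A plasma without T790M can arise in two ways: the resistant disease does not carry T790M, or the blood held too little tumor DNA to show any mutation. Tissue would help to separate the two, but section 8.7 itself calls this a plasma-only cohort and notes that metastatic lesions are seldom biopsied. The stated exclusions concern DNA yield, sample handling, pathology and analytical QC. None is described as a check that tumor-derived DNA is present.

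The patient's own sensitizing EGFR alteration could act as a within-sample control, because it should be visible whenever enough tumor DNA is in the tube. Section 8.4 does not specify that use. It does plan summaries of sensitizing against resistance alterations within a gene, but these are not stated to be paired within patient, checked against the known alteration, or specific to category B. The concordance tables in section 8.3 need tissue, so plasma-only patients do not enter them.

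At stake is how the detected rate can be read. The same ambiguity runs into section 8.7, which passes from the probability that a patient has T790M to the probability that plasma shows it, with no allowance for missed detection.

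**Working it through.** **Inputs.** n = 40 evaluable, prevalence 0.50, detected range 40% to 60% (16 to 24 of 40), and Clopper-Pearson intervals (sections 8.1 and 8.7). Plasma sensitivities of 0.90 and 0.80 are the true-PPA values used in section 8.7 for the concordance cohort. Applying them to T790M is my assumption, so a wider range is shown.

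**1. Reproduce the plan's figures.** 50 × 0.80 = 40. With X ~ Binomial(40, 0.50), P(16 ≤ X ≤ 24) = 0.846, against the stated 85%. Clopper-Pearson for 20/40 is 0.338 to 0.662, width 0.324, against the stated 0.32. Both agree. The binomial probability used is the prevalence itself, so the calculation implies a sensitivity of 1.00.

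**2. Allow for missed detection.** Detection probability = prevalence × sensitivity.

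| Sensitivity | Detection probability | Expected count of 40 | P(16 ≤ X ≤ 24) |
|---|---|---|---|
| 1.00 | 0.50 | 20 | 0.846 |
| 0.90 | 0.45 | 18 | 0.766 |
| 0.80 | 0.40 | 16 | 0.556 |
| 0.70 | 0.35 | 14 | 0.305 |
| 0.60 | 0.30 | 12 | 0.115 |

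**3. What an observed 40% would mean.** 0.40 = 0.40 × 1.00 = 0.50 × 0.80 = 0.80 × 0.50. The proportion alone identifies neither prevalence nor sensitivity.

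**4. What the cross-table would show.** Assume that every patient has a documented sensitizing alteration, that it is seen in a fraction f of plasmas whether or not T790M is present, and that T790M is found only in those plasmas and always when present there.

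| f | Sensitizing+ / T790M+ | Sensitizing+ / T790M− | Neither | Rate, all evaluable | Rate, sensitizing+ | Negatives that are non-informative |
|---|---|---|---|---|---|---|
| 0.90 | 18 | 18 | 4 | 18/40 = 45% | 18/36 = 50% | 4/22 = 18% |
| 0.80 | 16 | 16 | 8 | 16/40 = 40% | 16/32 = 50% | 8/24 = 33% |

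The 50% in the sixth column follows from the last assumption. If only 80% of T790M were found in the 32 sensitizing-positive plasmas, the count would be 32 × 0.50 × 0.80 = 12.8 and the rate 12.8/32 = 40%.

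**5. Precision of the restricted rate.** Clopper-Pearson at an observed 50%:
- 18/36: 0.329 to 0.671, width 0.342.
- 16/32: 0.319 to 0.681, width 0.362.
- If f fell to 0.60, 24 patients would remain and the width would be 0.418.

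**The case against.** The strongest reply is that objective 6.2.6 is to characterize detection in plasma, not to estimate prevalence or to rule T790M out. A detection rate in all evaluable plasmas does that, in a descriptive study with no hypothesis test. This stands, and it is why that rate should remain the main result. A reader might infer that the planned rate is the wrong answer to the objective; the wording of the objective does not support that.

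Next, section 8 is only a general description, and the SAP might contain the table. Section 8.4 also plans related summaries and a per-patient clinical action. This narrows the gap and rules out saying that the cross-table will not be done. It does not supply the table, and the one named statistic is the overall proportion.

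A reader might also call the double-negative samples assay failures. The documents do not support this: samples failing yield or analytical QC are already removed, and what remains is a valid sample that may carry little tumor DNA.

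The restricted rate is not the true T790M rate either. Step 4 shows that it falls when T790M is present only in a subclone and missed. The 80% and 90% values come from a cohort expected to be mostly newly diagnosed, not progressing on EGFR-targeted therapy.

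Finally, the control may be missing for some patients. Tables 3 and 6 list a mutation report, but section 7.3 collects marker status where available, and section 5.1 requires neither a report nor a sensitizing alteration. How many patients this affects cannot be told from the documents, so it calls for a separate row and supports no claim that the denominator is materially wrong.

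**Conclusion.** The point holds in a limited form. As specified, the T790M result in category B will be a valid detection rate whose negatives cannot be interpreted in patients without tissue at progression. Under the assumptions of step 4, 18% to 33% of negatives would be non-informative.

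The 85% in section 8.7 is not an arithmetic error, though it might be taken for one. It is correct for its inputs but holds only with 100% plasma sensitivity. At 90% and 80% it is about 77% and 56%, provided that the PPA planning values carry over to T790M.

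This is a secondary, descriptive objective, and the primary analysis is unaffected. It is worth correcting because the remedy uses the mutation reports already listed and EGFR calls from the same panel. The denominators should be fixed in advance: section 8.1 has the SAP final before the interim data lock, and section 8.6 says that interim results will not change it.

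**What to change.** In section 8.4 and the SAP, for objective 6.2.6:

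1. Keep the T790M detection rate in all evaluable category B plasmas as the main result.
2. Pre-specify a per-patient cross-table of T790M by the patient's documented sensitizing EGFR alteration as detected in plasma, with four cells:
   - sensitizing-positive, T790M-positive;
   - sensitizing-positive, T790M-negative;
   - sensitizing-negative, T790M-positive, counted as a T790M detection;
   - negative for both, labelled non-informative.
3. Show patients with no documented sensitizing alteration, or no mutation report, in a separate row.
4. Report the T790M rate among plasmas with the sensitizing alteration detected as a supplementary estimate. Note that subclonal T790M can still be missed, so it remains a lower bound on prevalence, sampling error and false positives aside. Extending it to the whole cohort also assumes that shedding of tumor DNA does not depend on T790M status.
5. In section 8.7, state the 85% as conditional on plasma sensitivity, with the values at 90% and 80% beside it.

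The cost is SAP wording and one extra table, with no new procedure or change in enrollment. The supplementary rate has a somewhat wider interval: about 0.34 to 0.36 with 36 to 32 informative patients, against 0.32 with 40. It will be wider still if reports are missing or if fewer plasmas show the sensitizing alteration.

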8.5 Exploratory Analyses

We will examine the association between the presence of alterations in plasma or tissue and endpoints such as time to progression and response to first therapy initiated after liquid biopsy.

Time to progression is defined as time from first initiated therapy (after liquid biopsy) to progression as documented by imaging or clinical evaluation. Progression identified at the time of death will be considered an event. Patients still on therapy one year after the liquid biopsy assessment will be censored. We will use Cox proportional hazards regression models and Kaplan-Meier analyses and will consider non-linear techniques, including smoothing splines. Subset analyses based on alteration status in tissue and plasma may be conducted.

CONFIDENTIAL – PROPRIETARY PROPERTY OF GENOMIC HEALTH, INC.

Study Protocol

Response is defined as best response to therapy initiated after liquid biopsy (complete response, partial response, stable disease or progressive disease). We will use logistic regression models and will consider non-linear techniques, including smoothing splines.

8.6 Interim Analysis

An interim analysis will be performed when approximately 30 patients with EGFR mutations in tissue samples are enrolled. Should the laboratory not have finalized analytical validation at that time, enrollment will continue until analytical validation has been performed. The interim analysis will support the documentation of performance of the Genomic Health liquid biopsy test and may be used for submission of an abstract to a scientific conference. The results of this interim analysis will not be used to modify the design or conduct of this study, including the associated Laboratory Protocol and Statistical Analysis Plan. In particular, the sample sizes specified in section 4 will not be modified based on the results of this interim analysis.

8.7 Sample Size

The sample size considerations for this study were based on the probability of observing PPA/NPA estimates in the anticipated range as well as the size of the confidence intervals around these estimates. To account for possible losses (~20%), approximately 260 patients with plasma and tissue samples will be enrolled to obtain approximately 208 patients with evaluable samples for concordance analyses and 50 patients with plasma samples only will be enrolled to obtain 40 evaluable patients to characterize the detection of *EGFR* T790M alterations in plasma. It is expected that the majority of patients with plasma and tissue samples will be newly diagnosed with stage IV non squamous NSCLC since metastatic lesions are not frequently biopsied.

In patients with plasma and tissue samples, two *EGFR* alterations, L858R and exon 19 deletion, are expected to be observed most often: each with ~45% prevalence in patients with *EGFR*-mutant tumors²⁹. The alteration-specific analyses for these alterations are expected to include ~25 evaluable patients each leading to a total of 50 patients with activating *EGFR* alterations. T790M resistance alteration has a low prevalence in untreated NSCLC³⁰ and hence is expected to be observed relatively rarely.

Figure 2 displays the 20th (blue) and the 30th (green) percentiles of the distribution of positive percent agreement as a function of the sample size using a binomial distribution and assuming a true PPA of 80%. Based on these results, a study with 25 patients with a known alteration will have a 70% probability to observe a PPA estimate

CONFIDENTIAL – PROPRIETARY PROPERTY OF GENOMIC HEALTH, INC.

[figure not shown]

Study Protocol

$\geq 75\%$. A study with 50 patients with a known alteration will have an 80% probability to observe a PPA estimate $\geq 75\%$.

Similar calculations for the true PPA of 90% indicate that a study with 25 marker positive patients will have a 75% probability to observe a PPA estimate $\geq 85\%$ (not shown in figure below). A study with 50 patients with a known alteration will have an 85% probability to observe a PPA estimate $\geq 85\%$.

Figure 2. Percentiles of the PPA estimate as a function of sample size assuming true PPA of 80%*

* Moving average smoother was applied to the estimates based on binomial distribution.
Legend: blue line represents 20% percentile and green line – 30% percentile of PPA estimates.

If a PPA of 80% is observed in 50 patients with a known alteration, the 95% exact Clopper-Pearson confidence interval will have a lower bound of 0.66 (Table 5). Similar logic applies to the NPA estimates. These calculations were obtained using PASS version 13.

CONFIDENTIAL – PROPRIETARY PROPERTY OF GENOMIC HEALTH, INC.

Study Protocol

Table 5. Lower bound of the 95% Clopper-Pearson confidence interval as a function of observed PPA estimate and sample size.

Observed PPA	Number of patients with detected alterations in tissue				
	20	30	40	50	60
0.90	0.68	0.74	0.76	0.78	0.80
0.85	0.62	0.67	0.70	0.72	0.73
0.80	0.56	0.61	0.64	0.66	0.68
0.75	0.51	0.56	0.59	0.61	0.62

In patients with plasma samples only who are progressing on EGFR targeted therapy (erlotinib, gefitinib, afatinib where tissue sample is not mandatory) approximately 50% of patients are expected to have T790M alteration. If the true probability of T790M alteration in this population is 0.50, we will have an 85% chance of detecting these alterations in 40% to 60% of samples from 40 patients progressing on EGFR targeted therapy (erlotinib, gefitinib, afatinib). In analysis with 40 patients, the width of the 95% confidence interval around the proportion of detected T790M alterations will be 0.32 if alterations are detected in 50% of plasma samples.

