	
gefitinib, afatinib) will be enrolled across the enrollment phases.
 
The sample size considerations are based on the probability of observing PPA/NPA estimates in the desired range as well as the size of the confidence intervals around these estimates. The results of the central tissue assessments will be used in analysis where available. In patients without central CLIA laboratory results, local assessments of genomic alterations in tissue will be utilized. We anticipate that ~20% of samples may be excluded from analysis due to insufficient DNA yield and/or pre-specified QC criteria.

Clinical Sites	Approximately 25 USA and International centers including centers in France, Germany, Ireland, Spain, United Kingdom, Japan, Chile and Mexico.
Inclusion/Exclusion Criteria	
Initially, approximately 200 patients will be enrolled regardless of genomic alteration status in tumor tissue (First Enrollment Phase). This will be followed by a Second Enrollment Phase including approximately 39 patients with clinically relevant alterations in EGFR and approximately 21 patients with alterations in ALK (EML4-ALK fusions) (as assessed in tumor tissue). In addition, approximately 50 patients progressing on erlotinib, gefitinib, or afatinib will be included across the enrollment phases (see Section 4, Figure 1).
 
Inclusion Criteria (all of the below)
 
 • Patients must be 18 years or older. • Patients with stage IV non squamous NSCLC who are either newly diagnosed or progressing on any treatment (progression defined as increasing tumor size or new metastatic lesions on clinical or imaging assessment). Patients with available tissue sample from a metastatic site or, if the patient presents with stage IV disease at diagnosis, from the primary tumor or a metastatic site. If a patient is progressing on EGFR targeted therapy (erlotinib, gefitinib, afatinib), tumor tissue sample is required only if available. • No new systemic anti-tumor therapy administered in the interval between the tissue biopsy and collection of the blood sample (interval not to exceed eight weeks). Local radiation therapy is permitted.

CONFIDENTIAL – PROPRIETARY PROPERTY OF GENOMIC HEALTH, INC.

	<h2>Study Protocol</h2>
---	-------------------------

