8. STATISTICAL METHODS

8.1 General Methods

This section provides a general description of the statistical analysis methods. A detailed description of the analysis methods will be provided in the Statistical Analysis Plan, that will be developed blinded to any analytical test results (i.e. from the liquid biopsy tests and tumor tissue assessments) and finalized prior to the data lock for the interim analysis.

This is a descriptive study to characterize the concordance between the results of the Genomic Health LBMP based on plasma and genomic assessment of the tumor tissue. Both the liquid biopsy and the tumor tissue assessments will report the status of the investigated alterations in a binary manner as detected or not detected. No formal hypothesis testing is planned. Unless otherwise stated, two-sided 95% Clopper-Pearson confidence intervals will be reported²⁸.

The analysis of a single tumor biopsy cannot yield a reference standard for a liquid biopsy assessment due to tumor multifocality and intra- and inter-tumor heterogeneity in stage IV disease. As described in the FDA Statistical Guidance on Reporting Results from Studies Evaluating Diagnostic Tests (2007), when a new test is evaluated by comparison to a non-reference standard, it is not possible to directly calculate unbiased estimates of sensitivity and specificity. Therefore, due to lack of reference standard for analysis of liquid biopsies, it would not be appropriate to describe the comparative results of the study in terms of sensitivity and specificity. Instead, we will characterize the concordance in terms of positive percent agreement (PPA) and negative percent agreement (NPA) as presented in section 8.3, Table 4.

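### Section 8.7 gives 70% as the chance of an observed PPA of at least 75% with 25 patients; the exact value is 78.0%, and two Table 5 lower bounds are 0.01 too high

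*Combined protocol and SAP*

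**What the plan says.** Section 8.7 opens with the basis for the study size: "The sample size considerations for this study were based on the probability of observing PPA/NPA estimates in the anticipated range", together with the width of the confidence intervals. The synopsis says the same ("The sample size considerations are based on the probability of observing PPA/NPA estimates in the desired range").

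The two commonest EGFR alterations, L858R and exon 19 deletion, are "expected to include ~25 evaluable patients each leading to a total of 50 patients" with activating alterations. Figure 2 "displays the 20th (blue) and the 30th (green) percentiles of the distribution of positive percent agreement as a function of the sample size", under a binomial model with a true PPA of 80%; a footnote says a moving-average smoother was applied. From that figure the text concludes that "a study with 25 patients with a known alteration will have a 70% probability to observe a PPA estimate" of at least 75%, and that 50 patients give 80%. For a true PPA of 90% and a threshold of 85%, it gives 75% with 25 patients and 85% with 50.

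Table 5 is titled "Lower bound of the 95% Clopper-Pearson confidence interval as a function of observed PPA estimate and sample size". This is the interval method set in section 8.1 ("two-sided 95% Clopper-Pearson confidence intervals will be reported"). In its row for an observed PPA of 0.90, the entries for 20, 30, 40, 50 and 60 patients are 0.68, 0.74, 0.76, 0.78 and 0.80.

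**The concern.** The 70% is worded as the probability itself, for exactly 25 patients, under a fully specified binomial model. It can therefore be checked directly, and it is 8 points below the exact value. Set beside the 80% given for 50 patients, it suggests that doubling the number of positives gains 10 points. The exact gain between those two sizes is 81.4 − 78.0 = 3.4 points. The case of 25 patients matters because it is the number the plan expects for each main alteration.

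The Table 5 slips go the other way: both overstate the lower bound. The entry for 60 patients shows a round 0.80 that 54/60 does not reach.

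What is at stake is the accuracy of a stated justification, which may be carried into later documents. No decision rule depends on these figures.

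**Working it through.** **Inputs.** True PPA 80% and 90%, thresholds 75% and 85%, and 25 or 50 tissue-positive patients (section 8.7); two-sided 95% Clopper-Pearson intervals (section 8.1); 69 patients with EGFR alterations enrolled (Table 2); about 20% of samples lost (section 4); about 45% prevalence for each main alteration (section 8.7).

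**Planned number per alteration.** 69 × 0.80 = 55.2 evaluable; 55.2 × 0.45 = 24.8. This reproduces the plan's figure of about 25.

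**Where the 70% comes from.** With X ~ Binomial(25, 0.80), P(X ≤ 17) = 0.109 and P(X ≤ 18) = 0.220.

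- The 20th percentile of the estimate is 18/25 = 0.72, below 0.75.
- The 30th percentile is 19/25 = 0.76, above 0.75.
- With centred moving averages over 3 to 21 neighbouring sample sizes, the 20th percentile is about 0.73 to 0.74 and the 30th about 0.76.

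Of the two plotted levels, only the 30th clears the threshold. That supports a probability of at least 70%.

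**The probability itself.** An observed PPA of at least 75% in 25 patients means X ≥ 19, since 0.75 × 25 = 18.75:

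P(X ≥ 19) = 1 − P(X ≤ 18) = 1 − 0.2200 = 0.7800.

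Other readings do not give 70% either: a cut-off of 20/25 gives 61.7%, a cut-off of 18/25 gives 89.1%, the normal approximation gives 73.4%, and averaging the tail probability over 3 to 11 neighbouring sizes gives 74.9% to 77.9%.

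**Sensitivity to the sample size.** P(observed PPA ≥ 75%) at a true PPA of 80%:

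| n | 20 | 21 | 22 | 23 | 24 | 25 | 26 | 27 | 28 | 29 | 30 |
|---|---|---|---|---|---|---|---|---|---|---|---|
| % | 80.4 | 76.9 | 73.3 | 69.5 | 81.1 | 78.0 | 74.7 | 71.3 | 81.8 | 79.0 | 76.1 |

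**All four stated probabilities.**

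| True PPA | n | Event | Stated | Exact |
|---|---|---|---|---|
| 80% | 25 | X ≥ 19 | 70% | 78.0% |
| 80% | 50 | X ≥ 38 | 80% | 81.4% |
| 90% | 25 | X ≥ 22 | 75% | 76.4% |
| 90% | 50 | X ≥ 43 | 85% | 87.8% |

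All four are floors at the stated size. The last three lie within 3 points of the exact value.

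**Table 5.** The lower bound is the 0.025 quantile of Beta(x, n − x + 1), with x = observed PPA × n.

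- The bound the text relies on, 40/50: 0.6628, printed 0.66. Reproduced.
- 27/30: 0.7347, which rounds to 0.73; printed 0.74.
- 54/60: 0.7949, which rounds to 0.79; printed 0.80.

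The other 18 of the 20 cells agree to two decimals. Four of those 18 (0.85 and 0.75 at 30 and at 50 patients) correspond to half-integer counts such as 25.5/30. They agree when the formula is evaluated at the fractional count, although no real sample can produce that result.

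**The case against.** The strongest reply is that the 70% is a percentile reading, not a failed calculation. The text ties it to Figure 2, which shows only two percentile levels, and 70% is the one that those curves support at 25 patients. The figure is not visible in the text available and the smoothing window is not given, so the reading itself cannot be checked. In addition, the plan expects only about 25 patients per alteration and the exact probability is saw-toothed, so a rounded conservative figure may serve the reader better than a precise 78%.

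Most of this stands. It explains the figure and shows that it is safe as a floor at 25 patients. It does not justify wording a floor as the probability, and the smoothing footnote belongs to the figure while the sentence names exactly 25 patients. Even as a floor, 70% is not strict throughout the neighbourhood: at 23 patients the value is 69.5%.

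On Table 5, both printed cells exceed the unrounded bound by only about 0.005. Rounding twice (0.7347 to 0.735 to 0.74; 0.7949 to 0.795 to 0.80) would account for both, though that cause is inferred. Neither cell is the case of 50 patients that the text uses. The slips are small, but they remain wrong entries in a table whose definition is clear.

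**Conclusion.** The point holds, as a minor correction. At 25 patients and a true PPA of 80%, the probability is 78.0% and not 70%; the stated figure is valid only as a lower limit. Two of the 20 cells in Table 5 are 0.01 too high after rounding. These results rest on the plan's own binomial model, thresholds and interval method, with no outside assumption.

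The practical effect is confined to correct reporting. The probability errs on the conservative side, the study is descriptive with no formal hypothesis test, and the reported intervals will be computed from the observed data. The sample size and the analyses stand.

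**What to change.** In section 8.7, either state that the probability is at least 70% with 25 patients, or give 78% with 25 patients and add that it runs from about 70% to 82% for 20 to 30 patients. For consistency, word the other three probabilities as lower limits at the stated sizes (exact values 81.4%, 76.4% and 87.8%). In the 0.90 row of Table 5, change the entry for 30 patients to 0.73 and the entry for 60 patients to 0.79.

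This costs nothing beyond the edit: a few words and two table cells, with no effect on enrolment, procedures or analysis.
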